## 1 Background

In 2014, 1.2 million lives were lost to HIV and AIDS, while 2.0 million people became newly infected[1]. The majority of the burden is in Sub-Saharan Africa, where 71% of the global total of people living with HIV reside[2]. Zimbabwe is one of the worst affected countries with an HIV prevalence of 15% and an estimated 54,994 AIDS related deaths in 2014[3]. Interventions to prevent and treat HIV remain important in efforts to contain the epidemic. Key to these efforts is HIV testing which is the gateway to accessing interventions for prevention and/or treatment of HIV. Recent evidence of effectiveness of early treatment of HIV [4, 5] and the subsequent 2015 WHO "treat all" recommendations make it critical to optimise methods of identifying HIV infected individuals. UNAIDS have set global treatment targets, 90-90-90, that require that by 2020, 90% of people living with HIV are diagnosed, of whom 90% are on treatment and that 90% of those on treatment are virally suppressed[6]. Many settings are still far from reaching the first HIV testing target: globally it is estimated that only 54% of people living with HIV are aware of their status[6]. In Zimbabwe, the 2010/11 Demographic and Health Survey found that among individuals who tested HIV positive, 63.7% had previously tested (71% for women and 51.5% for men)[7]. Of note this survey was done a long time ago so these figures are likely to be out of date. Rates of HIV testing are lowest among men, adolescents and marginalised groups such as sex workers.[7] Barriers to testing include concerns about stigma, fear of prognosis, lack of awareness of HIV risk, and the inconvenience, transportation and opportunity costs incurred.[8, 9] Innovative models of provision of HIV testing services are required to ensure that all those infected benefit from treatment, thereby reducing their risk of onward sexual or vertical transmission.

## **1.1 The potential for HIV Self-testing**

HIV self-testing is a process where an individual collects their own sample and conducts their HIV test privately without a provider present. It has potential to substantially scale up acceptability and access to testing both in the general population as well as in hard-to-reach populations such as sex workers, in a manner that is low-cost, confidential, and empowering for users. Rapid testing technologies include simple-to-use oral HIV tests that offer high sensitivity and specificity, ideal for self-testing strategies.[10, 11] Early research suggests that self-testing is acceptable, with high uptake and accuracy of results. For example, in a community-based study in Malawi, 92% of participants opted for supervised self-testing over standard provider-delivered HIV testing and counselling (PDHTC), including a high proportion of men and first time testers, key groups that are historically reluctant to test. In the same country, the performance characteristics of the oral fluid test (Oraquick Advance) were acceptable with estimated sensitivity from two studies of 97.9% and 93.6% and specificity of 100% and 99.9% respectively. [12, 13] Similarly good accuracy results were found among rural and urban participants in South Africa[14]. Preliminary research in Zimbabwe also found that urban and rural participants were able to produce accurate self-test results using both written and video instructions[15].

Key stakeholders in the HIV testing field including policy makers, health care workers, academics and activists have welcomed the idea of self-testing but caution on the need for research and policy guidance before scale up[16]. Globally the adoption of self-testing into policy is at varying stages. A few countries have HIV testing policies which include self-testing, e.g. Australia, China, France, Kenya

and United States while others such as Zimbabwe, Malawi and Zambia are still considering it[17]. WHO needs more research before they can issue normative guidance on self-testing, but they have recommended that countries go ahead with demonstration projects, which Zimbabwe Ministry of Health and Child Care is interested in. Important questions to be asked before scale-up of self-testing include: 1) how self-test kits can be regulated, marketed and distributed, 2) how to ensure protection from social harms such as forced testing and gender based violence, 3) how can linkage to post-test services after testing be optimised, and 4) what is the relative cost and cost effectiveness of different self-testing models.

## 1.2 Regulation, Marketing and Distribution of Self-tests

Because results of an HIV test can have significant implications for mental health, health seeking, sexual behaviour and transmission, it is necessary that self-testing be well regulated. This includes regulation of the quality standards of the self-test kits, how and where kits are distributed and by whom, and the nature of marketing/advertising messages[18]. There is evidence that trained community health workers can be useful in distributing self-test kits and providing instructions and support to self-testers [13, 17]. In a study that is being conducted in rural Zimbabwe, community-based distribution of test kits by trained lay health workers is being piloted. This will enable us to refine our implementation strategies for community distribution of self-test kits.

## **1.3 Ethical Issues during implementation of self-testing**

Although concerns have been raised about the potential for social harms such as suicides and intimate partner violence following self-testing [19, 20], in practise there is little evidence that such harm happens [13, 20]. In the self-testing study in Malawi, neither intimate partner violence nor suicides were reported. The prevalence of forced testing, often by main partners, was found to be 3%, although forced testers generally did not regret having tested [13]. Despite this promising evidence it is important that procedures are set in place to prevent, monitor and detect any social harm that may result from self-testing. Importantly, such harms may be difficult to detect, underscoring the need for innovative surveillance methods. In this study we will have ongoing surveillance for social harms using methods developed from the pilot self-test distribution study mentioned above (the pilot study will be done in Mazowe district and has been approved by MRCZ, London School of Hygiene &Tropical Medicine and UCL ethics committees, refs MRCZ/A/2023, 10533 and 5367/001 respectively).

## **1.4 Linkage to care following self-testing and cost effectiveness**

Because the value of testing comes from ability to link to prevention and/or treatment services, it is important to determine how well self-testers link to post-test services and to implement interventions for optimising linkage. Previous research has shown that self-testers link as well as individuals who tested using other models [13]. Optimal linkage rates are not only important for the health of HIV positive individuals but also for the cost effectiveness of the self-testing intervention. A 2015 modelling study found that for a country like Zimbabwe self-testing may be cost-effective; however cost effectiveness can be negatively affected by poor rates of linkage to care after testing[21]. It is therefore important to address barriers to linkage, which include fear of disclosure (and subsequent stigma), long waiting times at health facilities, distance to health facility, travel costs and user costs

[22]. Social support, including from lay health workers, has been found to be effective in facilitating linkage to care. In this study we aim to determine whether incentivising community-based kit distributors according to number of clients who link to post-test services will improve linkage to post-test outreach services in rural communities. We will also determine the cost and cost effectiveness of self-testing interventions with various models of facilitating linkage to care.

## 2 AIM OF THE STUDY

The study is being conducted under a consortium, HIV Testing Africa (STAR) that is investigating models of distributing HIV self-test kits in three countries, Zambia, Malawi and Zimbabwe. The aim of the study is to determine the acceptability and feasibility of community-based distribution of HIV self-test kits in rural Zimbabwean communities.

## Primary Objective

• To determine whether incentivising community based distributors (CBDs) to support selftesters is effective in improving uptake of self-testing and linkage to post-test services

## Secondary Objectives

- To determine the effect of self-testing on HIV testing rates in rural Zimbabwean communities
- Using a discrete choice experiment, to explore client preferences for program characteristics that facilitate linkage to care after self-testing
- Using time-series methods, to evaluate the impact of CBD incentivisation on rates of ART initiation in districts where HIVST kits are distributed
- Using a difference-in-differences approach, to evaluate the effect of HIV self-testing on rates of ART initiation in the study districts
- To determine incidence of gender-based violence in communities where self-test kits are distributed
- To pilot the distribution of HIV self-test kits at both static and mobile HIV testing centres and through voluntary medical male circumcision services
- To explore barriers and enablers to development of a national policy for the regulation, marketing and distribution of self-test kits among stakeholders providing/regulating HIV services in Zimbabwe
- To qualitatively explore feelings about self-testing and linkage to care among clients, health care workers and community-based kit distributors
- To determine the cost and cost effectiveness of community-based distribution of HIV self-test kits

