- III. Refining procedures for facilitating and documenting linkage to prevention and care services after self-testing.

A detailed process evaluation will be conducted throughout the program implementation period.

Quasi experimental methods will be used to evaluate the effect of incentives for CBDs on ART initiations in each study district, and the overall effect of HIVST kit distribution on ART initiations.

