## 4.2.2 Randomisation

Thirty-eight outreach communities in the seven study districts will be randomised in a 1:1ratio to receive incentives for CBDs or no incentives. Randomisation will be performed by the study statistician. Restricted randomisation will be used to minimise imbalance in key factors between arms (district, HIV prevalence and proximity to a health facility). A public randomisation ceremony will be held to select the final allocation from a randomly-generated list of acceptable allocations.

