#### Analysis of health facility data

To evaluate the effect of CBD incentivisation on ART initiations, trends in number of ART initiations in the following facilities will be compared, and difference-in-difference estimates will be computed:

- Facilities with catchment areas where HIVST kits were distributed and CBDs were incentivised
- Facilities with catchment areas where HIVST kits were distributed and CBDs were *not* incentivised

To evaluate the overall effect of HIVST on ART initiations, trends in number of ART initiations in the following facilities will be compared, and difference-in-difference estimates will be computed:

- Facilities with catchment areas where HIVST was offered
- Facilities with catchment areas where HIVST was not offered

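### The protocol names two different methods for the incentive effect on ART initiations, calls a randomised contrast quasi-experimental, and leaves the unit of analysis unclear

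*Protocol*

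**What the plan says.** Three places in the protocol describe how the effect on ART initiations will be analysed.

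- **Secondary Objectives.** For incentives: "Using time-series methods, to evaluate the impact of CBD incentivisation on rates of ART initiation in districts where HIVST kits are distributed". The next bullet, on self-testing itself, reads: "Using a difference-in-differences approach, to evaluate the effect of HIV self-testing on rates of ART initiation in the study districts".
- **Section 3, Overall research strategy.** "Quasi experimental methods will be used to evaluate the effect of incentives for CBDs on ART initiations in each study district". The same sentence covers the overall effect of kit distribution.
- **Section 6, Analysis of health facility data.** For incentives: "To evaluate the effect of CBD incentivisation on ART initiations, trends in number of ART initiations in the following facilities will be compared". The sentence goes on to name difference-in-differences as the estimator. One of the two groups is "Facilities with catchment areas where HIVST kits were distributed and CBDs were incentivised". The other is the matching set without incentives. The same method is then given for facilities with and without self-testing.

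Section 4.2.2 randomises 38 wards in seven districts 1:1 to incentives or none, and states: "Restricted randomisation will be used to minimise imbalance in key factors between arms (district, HIV prevalence and proximity to a health facility". Section 4.2.4 abstracts monthly counts from every health facility in each study district for the six months before kit distribution, the distribution period and the three months after it.

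**The concern.** The objectives attach one method to incentives and another to self-testing. The analysis section attaches the second method to both. An analyst could follow either text, so the estimator for a named secondary objective could be chosen after the data are seen.

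Two further points add to the ambiguity. First, the objectives and Section 3 speak of districts, whereas the analysis section groups facilities by the incentive status of their catchment. Incentives vary between wards within districts, so the choice of unit decides whether the contrast can be estimated. Second, the quasi-experimental label suits self-testing versus no self-testing, which was not randomised. It does not suit incentives versus none, which was. The label passes over the main strength of the design for this question.

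**Working it through.** The protocol gives no figure to reproduce here. The check sets the texts side by side and then asks what each reading would deliver.

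**1. The texts compared**

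| Place | Incentive effect | Self-testing effect | Geography or unit |
|---|---|---|---|
| Secondary Objectives | Time-series | Difference-in-differences | Districts |
| Section 3 | Quasi-experimental, unspecified | Quasi-experimental, unspecified | Each study district (incentives) |
| Section 6, health facility data | Trends compared, difference-in-differences | Trends compared, difference-in-differences | Facilities by catchment |

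The named method for incentives differs between the first and third rows. The unit differs or is left open.

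**2. What district totals would give, if they were used**

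Inputs: 38 wards and seven districts (Sections 4.2.1 and 4.2.2), so 38/7 = 5.4 wards per district on average. The number in each district is not stated, so the splits below are assumptions.

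- *Do districts mix the arms?* Simulating unrestricted 19:19 allocation, all seven districts hold both arms with probability about 0.79 for a split of 6, 6, 6, 5, 5, 5, 5, and about 0.33 for 10, 8, 6, 5, 4, 3, 2. The probability is 0 if any district has a single ward. Balancing on district pushes towards mixing but does not guarantee it everywhere.
- *Equal shares.* Regress the change in each district's total on an intercept and the share of its wards that are incentivised. If every share is 0.5, the design matrix has rank 1 and the incentive effect is not identified.
- *Slightly unequal shares.* With shares 0.5, 0.5, 0.5, 0.4, 0.6, 0.4, 0.6 the rank is 2. The sum of squared deviations is 4 × 0.1² = 0.04, so the standard error of the incentive slope is s/√0.04 = 5s, where s is the residual standard deviation of the district changes. The effect is formally estimable from seven points over a range of 0.2, but practically uninformative.

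**3. Difference-in-differences against baseline adjustment for the randomised contrast**

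Take one pre and one post value per facility, with equal variance σ² and correlation r, and ignore the small cost of estimating the slope.

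- Change score: variance 2σ²(1 − r).
- Baseline-adjusted: variance σ²(1 − r²).
- Ratio: (1 − r²)/[2(1 − r)] = (1 + r)/2.

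At assumed r = 0.3, 0.5 and 0.9 the ratio is 0.65, 0.75 and 0.95. Baseline adjustment is never less precise under these assumptions, but the saving falls from 35% to 5% as r rises. The protocol gives no value of r.

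**4. Periods**

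The study timeline shows kit distribution over 12 months. Section 4.2.4 does not say whether before, during and after refer to the whole study or to each ward. Only if they were study-wide, with ward starts spread evenly, would about half of the facility-months in the distribution period precede local exposure.

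**The case against.** The best defence is that all three texts describe one analysis at different levels of detail. The health facility section says "trends in number of ART initiations in the following facilities will be compared, and difference-in-difference estimates will be computed". Comparing monthly facility trends between two groups before and after an intervention is a form of controlled time-series analysis. The phrases about districts can simply say where the facilities are, and the data are collected by facility. Difference-in-differences between groups defined by randomisation is valid. Facilities were not themselves randomised, and the protocol does not say that catchments coincide with wards, so a cautious label is defensible. Alignment of months to exposure is commonly left to a statistical analysis plan.

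Much of this stands. A reader might infer that a district-level time-series analysis is planned, that every district must hold both arms, and that the incentive effect therefore cannot be estimated. The documents support none of these as stated: no text sums counts to districts, Section 4.2.2 only minimises imbalance on district, and strict non-identification needs equal shares. A reader might also infer that the effect would be diluted by half. That rests on study-wide periods and even starts, neither of which is stated.

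The defence does not remove the conflict in the objectives themselves. They place time-series and difference-in-differences in adjacent bullets for different questions, so the labels were meant to differ. For facilities whose catchment is a randomised ward, incentive status is set by the randomisation, whatever the analysis is called.

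**Conclusion.** The protocol contradicts itself on the method for this secondary objective, mislabels a randomised contrast as quasi-experimental, and leaves the unit of analysis unclear. One possible reading, district totals, would make the incentive effect unidentifiable or nearly so. This is a risk created by the wording, not an analysis that the protocol prescribes.

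The facility-level difference-in-differences is not biased by design for the randomised contrast. The case for baseline adjustment is precision: a variance of 65% to 95% of the difference-in-differences variance for r between 0.3 and 0.9, under equal variances and a single pre and post value. Since r is unknown, the gain may be as small as 5%. Dilution through timing is a risk only if the periods are not ward-specific, which the protocol does not say. The primary outcome, the sample size and the main trial model are unaffected.

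**What to change.** State one analysis of the incentive effect and use it in the Secondary Objectives, Section 3 and the health facility part of Section 6:

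- Outcome: monthly ART initiations in facilities whose catchment is a randomised ward.
- Contrast: randomised arm, from that ward's own kit start.
- Adjustment: the facility's level in the six months before kits, allowing for clustering by ward.
- Wording: say that district only locates the facilities. Drop the time-series and quasi-experimental labels for incentives. Keep difference-in-differences for the non-randomised comparison of self-testing with no self-testing.

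The cost is a wording change and a list linking facilities to wards, which the catchment groups already in Section 6 need anyway. No new outcome data are required: monthly facility counts are already to be abstracted, and the CBD forms in Section 4.2.9 record the date of kit delivery.

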## **3 OVERALL RESEARCH STRATEGY IN ZIMBABWE**

We plan to deliver HIV self-test kits to households in rural communities using communitybased distributors (CBDs). CBDs will be trained to provide assistance to help people self- test if requested /required. CBDs will encourage people who self-test to link to post-test services provided by PSI Zimbabwe in their communities at either 1-2 weeks or 3-4 weeks after self-test kit delivery (See figure 1). We propose to conduct a clusterrandomised trial in 38 rural outreach communities in order to

test whether incentivising community based distributors (CBDs) according to number of clients who attend outreach services at weeks 1-2 and weeks 3-4 after self-test kit delivery increases testing uptake and linkage to post-test services. Sites will be randomised to incentives for community based distributors (CBDs) to link self-testers to post-self-test care or no incentives. (See figure 2). Six weeks after the first PSI outreach visit, community-based surveys will be conducted in four randomly selected enumeration areas (EAs) in each outreach community. Survey participants will be asked about whether they were offered self-test kits, whether they used them and their linkage to post-test services. In addition, to verify self-reports dried blood blot (DBS) samples will be taken for testing for HIV, viral load, recent infection and ARV levels. Study outcomes will be assessed programmatically and through the survey.

Figure 2	2: Stud	y design						
38 PSI outreach sites Random allocation of 19 sites per arm								
CBDs deliver self tes	∳ st kits t	o rural households						
6								
CBDs incentivised to link self testers to care	Process E\ Program da	CBDs not incentivised to link self testers to care	4 EAs					
PSI provide post-test services 1-2 and 3-4 weeks post test distribution PSI provide post-test services 1-2 and 3-4 weeks post test distribution								
Primary outcome – measured through survey (not programme) % self-report linked to PSI/govt clinic for any reason								
Secondary outcomes – measured through survey (not programme) % who report self-testing % who linked to PSI % men taking up VMMC								
% self-report linked % initi	l for co ated on	nfirmatory testing ART	s per					

Before randomisation, formative work with the following aims will be conducted:

- I. Understanding client/user preferences for HIV self-testing services
- II. Maximising detection of social harms as a result of HIV self-testing
- III. Refining procedures for facilitating and documenting linkage to prevention and care services after self-testing.

A detailed process evaluation will be conducted throughout the program implementation period.

Quasi experimental methods will be used to evaluate the effect of incentives for CBDs on ART initiations in each study district, and the overall effect of HIVST kit distribution on ART initiations.

## Primary outcome assessed in representative population based survey

• Proportion of individuals who report attending PSI outreach services or any health facility following HIV self-test kit distribution

## Secondary Outcomes assessed in the survey

- Proportion of individuals reporting that they have self-tested in each community
- Proportion of people who report that they linked to PSI outreach services
- Proportion of men who report taking up VMMC in each community

- Proportion of those with reactive HIV self-tests who report linkage to confirmatory testing regardless of site
- Proportion of HIV positives initiated on ART

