## 4.2.4 Description of study interventions

## Incentives for CBDs

During training, CBDs in communities that have been randomised to CBD incentives for linking selftesters to post-test services will be told that they will get a stipulated amount of money (20c) for each self-tester who attends the PSI outreach site after testing. Upon attendance at outreach sites, all clients who report having self-tested will be asked to show their self-completed appointment card (which bears the CBD identity number) to PSI staff. Staff will keep a log of clients that attend according to CBD in order to facilitate payment of the CBD. If a client has not brought their appointment card, they will be asked to provide the name of the CBD who supplied the self-test kit, which will be verified with CBD kit distribution records in that area before the CBD is credited with the attendance.

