Furthermore, survey participants will be asked to give a finger-prick blood sample that is collected on dried blood spot filter paper according to standards set by the United States National Committee for Clinical Laboratory Standards (NCCLS) published in "Blood Collection on Filter Paper for Neonatal Screening Programs" (LA4-A; 1997). The samples will be air dried onto filter paper and stored at room temperature until they are transported to PSI Zimbabwe's laboratory in Harare for HIV-1 antibody testing using validated testing algorithms. The filter papers will be labeled with unique barcodes that are also entered into the tablet for the corresponding questionnaires to ensure that survey data can be linked to laboratory results. Identifying information will be collected on the consent form, which will not be linked with survey materials. DBS samples will be stored at -20°C and then tested in batches. They will be tested serially for HIV-1 antibody with discrepant results resolved by PCR. Testing for viral load will be carried out on all samples which are HIV antibody positive on DBS (as well as a sub-set of those HIV antibody negative) using the Abbot Real Time HIV-1 m2000 viral load assay. All samples that are confirmed HIV infected will be tested using a qualitative assay for the following antiretroviral drugs Efavirenz, Nevirapine, Lopinavir and Atazanavir. Samples that are confirmed HIV positive will also be tested for recency of HIV infection using the lag avidity assay. The tests will be conducted at local laboratories in Zimbabwe. In the event that it is not possible to get local tests for drug levels and recency of infection, samples will be shipped for testing at a South African laboratory. Participants will be asked to consent for specimen shipment.

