#### Cluster randomised trial

The main statistical analyses for the cluster randomised trial will include (i) descriptive analyses of community characteristics by arm; and ii) outcome evaluation of the primary and secondary outcomes. Analyses will be intention-to-treat. A random effect will be included to account for clustering at site level. For binary outcomes, a random effects logistic regression model will be used. Intervention arm will be included as a covariate, and the model will adjust for cluster-level HIV prevalence and other key characteristics.

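### Linkage among people with a reactive self-test is compared in a group the incentive is expected to change, so an arm difference may reflect who tested and not who linked

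*Protocol*

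**What the plan says.** The list of secondary outcomes assessed in the survey (Protocol section 3) includes "Proportion of those with reactive HIV self-tests who report linkage to confirmatory testing regardless of site" and "Proportion of HIV positives initiated on ART". The first is restricted to people who self-tested and had a reactive result. The second has no window for the ART start and does not say how people already on ART are handled.

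The same document expects the incentive to act on testing itself:
- The Primary Objective asks whether incentivising distributors "is effective in improving uptake of self-testing and linkage to post-test services".
- Section 3 says the trial tests whether incentives "increases testing uptake and linkage to post-test services".
- Under Incentives for CBDs (section 4.2.4), distributors are paid "for each self-tester who attends the PSI outreach site after testing", so both testing and attending are rewarded.
- Self-testing is a separate survey outcome: "Proportion of individuals reporting that they have self-tested in each community".

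For the trial analysis, section 6 states "Analyses will be intention-to-treat" and specifies random effects logistic regression adjusted for cluster-level HIV prevalence and other characteristics. The survey (section 4.2.6) asks participants for a DBS sample for HIV testing, whether or not they self-tested, and collects ART experience by questionnaire.

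**The concern.** Randomisation makes the wards, and the people living in them, comparable between arms. It does not make those who chose to self-test comparable when the intervention changes who makes that choice. If the incentive draws in more hesitant people, the reactive group in the incentive arm contains a type of person largely absent from the same group in the control arm. An incentive that leads more HIV-positive people to confirmatory testing could then appear to reduce linkage. If the added testers are unusually ready to link, it could appear to improve linkage behaviour that it did not touch. Adjusting for ward-level prevalence does not address selection of individuals into testing.

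The ART outcome raises a different and smaller issue. Its wording allows starts from before kit distribution to count, and the incentive cannot have influenced those.

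**Working it through.** **Plan's own figures.** The Protocol gives no power or expected value for either outcome. Its power table concerns primary-outcome linkage. With c = 19 wards per arm, m = 200, k = 0.3 and two-sided alpha 0.05 (assumed, since none is stated), the formula is

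power = Φ( √{ (c−1)(p1−p0)² / [p0(1−p0)/m + p1(1−p1)/m + k²(p0²+p1²)] } − 1.96 ).

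It gives 91.8%, 83.3% and 87.2% against the stated 92%, 83% and 87%. These figures reproduce and are not in question. The formula is reused below for ART.

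**Reactive self-test denominator.** The documents give no uptake or linkage rates among positives, so all rates here are assumptions. Let u0 and u1 be self-test uptake among HIV positives in the control and incentive arms. Let a be linkage among people who would test in either arm, and b linkage among people who test only because of the incentive. Suppose the incentive adds testers, removes none and changes nobody's tendency to link once tested. Then:
- Conditional proportion, control arm: a.
- Conditional proportion, incentive arm: [u0·a + (u1−u0)·b] / u1.
- Difference: (u1−u0)/u1 × (b−a).
- Over all HIV positives: u0·a in control, u0·a + (u1−u0)·b with the incentive.

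| u0 to u1 | a, b | Conditional | Over all HIV positives |
|---|---|---|---|
| 40% to 60% | 50%, 20% | 50% to 40% | 20% to 24% |
| 40% to 50% | 60%, 30% | 60% to 54% | 24% to 27% |
| 40% to 60% | 60%, 30% | 60% to 50% | 24% to 30% |
| 40% to 60% | 60%, 60% | 60% to 60% | 24% to 36% |
| 40% to 60% | 30%, 60% | 30% to 40% | 12% to 24% |

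First row: (0.40×0.50 + 0.20×0.20)/0.60 = 0.24/0.60 = 0.40, against 0.50. Over all positives it is 0.24 against 0.20. Across these rows the conditional difference runs from −10 to +10 points, and is zero when added testers link as well as the others. The unconditional proportion rises in every row, as it should when more positives are tested and some of them link.

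**ART outcome.** Inputs are 15% prevalence (Background) and 200 respondents per ward, so 0.15×200 = 30 positives per ward if all give a sample. The share s already on ART is not given; 40% to 80% is assumed. New starts among the rest are assumed to double from q = 10% to 20%.
- If earlier starts count, the outcome is s + (1−s)q. For s = 40%: 46% against 52%, ratio 1.13. For s = 50%: 55% against 60%, ratio 1.09. For s = 80%: 82% against 84%, ratio 1.02. Power falls from 18% (s = 40%) to 4% (s = 80%) at k = 0.3. That k may be too large for proportions this high; at k = 0.1 power falls from 41% to 8%.
- If only new starts count over all positives, the ratio stays 2.0 and power runs from 86% down to 46% at k = 0.3.
- If people on ART before distribution are also left out (18 down to 6 respondents per ward), power runs from 88% down to 51%.
- If the incentive has no effect, q is equal in both arms and the difference is zero under every definition.

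**The case against.** Several counter-arguments have force.

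- **Other outcomes guard against misreading.** The primary outcome and the survey outcomes on self-testing and PSI linkage use all individuals, so a fall in conditional linkage would be read beside uptake and overall attendance. This limits the harm, but does not turn the listed outcome into a comparison of like with like.
- **The uptake gap is hypothetical.** Kits go to all households in both arms, so uptake may differ little, and with no difference there is no distortion. This stands. The point rests on the Protocol's own expectation that uptake will rise.
- **Intention-to-treat.** A reader might infer that the outcome contradicts the intention-to-treat statement. That is too strong: analysing wards as allocated can satisfy it. Doing so does not protect a denominator selected after allocation.
- **ART.** A reader might infer that the ART outcome also breaks the randomised comparison. The documents do not support this. HIV positives found by DBS are not selected by self-testing, so at worst the effect is diluted, and only if initiated is read to include earlier starts. Nor do the documents support saying that most positives were already on ART, as they give no coverage figure. New starts are also counted in PSI programme data and in facility records, with difference-in-difference estimates by incentive status.
- **Analysis plan.** A statistical analysis plan, not shown, may settle the ART window. The reactive-test denominator is already fixed in the Protocol.

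**Conclusion.** The point holds for the reactive self-test outcome. Its denominator depends on behaviour the trial sets out to change, so a difference between arms cannot be read as an effect on linkage. The distortion depends on how far uptake differs and how added testers differ from the rest. Neither is in the documents, so the 10-point swings are illustrations on assumed rates and no direction can be predicted.

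For the ART outcome only a narrower statement holds. The missing start window leaves room for a reading that loses sensitivity, but it creates no spurious difference.

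Both are secondary outcomes. The changes are worthwhile because they are cheap, not because the trial's main conclusion is at risk.

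**What to change.** **Reactive self-test outcome.** Define the arm comparison as the proportion who report a reactive self-test followed by confirmatory testing after kit distribution, over all survey participants or all DBS-positive participants, with the choice stated in advance. Keep the proportion among reactive self-testers as a descriptive figure, shown beside uptake in each arm.

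This needs a change of definition and no new samples. The unconditional proportion is smaller: in the first illustration, over all respondents, it would be 0.15×20% = 3.0% against 0.15×24% = 3.6%. It also mixes uptake with linkage, and DBS positives include people already diagnosed, for whom confirmatory testing may not be the relevant step.

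**ART outcome.** Count only ART starts reported after kit distribution among DBS-positive respondents, using a self-reported start date. Add a supporting analysis that leaves out those reporting ART before distribution. The cost is one questionnaire item if the date is not already asked, and some misreporting.

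The antiretroviral assay on the survey sample should not define prior ART. The survey takes place six weeks after the first outreach visit, which is itself one to two weeks after distribution. The sample is therefore taken about seven to eight weeks after distribution, and people who started in that interval can also test positive. Excluding them would remove the starts being counted.
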